2.3 Benefit-risk Assessment

The subject population will be composed of subjects with mild to moderate psoriasis; their psoriasis is expected to be manageable with topical therapy.

The active ingredients in the investigational products (CAL and BDP) are known to be effective for the treatment of psoriasis. The safety and efficacy profiles for marketed products with these ingredients (formulated as ointment, gel/topical suspension and more recently aerosol foam) are well known. A cream formulation of CAL and BDP may benefit subjects by providing improved convenience and ease of use resulting in increased patient adherence to therapy which will improve real-life treatment outcome (22).

According to the SmPC for Daivobet gel, the common AE (>1%) is pruritus. Uncommon (i.e. $\geq 0.1\%$ and < 1%) AEs are folliculitis, skin infections, exacerbation of psoriasis, dermatitis, erythema, rash, skin irritation, skin burning sensation, application site pain, as well as eye irritation (probably related to use on scalp).

The available data on MC2-01 cream suggest that MC2-01 cream will display a similar safety profile as the approved CAL/BDP topical products. A Phase 3 trial with MC2-01 cream and a maximal usage trial in adults have completed enrolment. As of the cut-off date of this clinical trial

MC2 Therapeutics

protocol, the adverse event reported is as expected and no serious unexpected serious adverse reactions (SUSARs) have been reported.

A subset of subjects will receive a cream vehicle. There is a risk that psoriasis symptoms may worsen in these vehicle-treated subjects; while an exacerbation of psoriasis may be inconvenient, it would not put the subjects at undue risk. In case of inadequate efficacy, the subject can decide to withdraw and then receive alternative therapy according to her/his choice.

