8.0 STATISTICAL METHODS AND DETERMINATION OF SAMPLE SIZE STATISTICAL AND ANALYTICAL PLANS

8.1 General Considerations for Data Analysis

The methodology presented below represents a brief overview of the statistical methods that will be fully detailed in the statistical analysis plan (SAP). The SAP will be finalised before the database is locked. Any changes to the methods described in the final SAP will be described and justified in the clinical trial report. All statistical analyses will be performed using SAS® statistical software (Version 9.2 or higher). Statistical significance will be tested at the 2-sided 5% level unless otherwise specified.

Subjects will be randomised in a 3:1:3 ratio (MC2-01 cream: MC2-01 cream vehicle: active comparator), stratifying by trial site. The aim is to randomise 14 subjects or more at each site. Furthermore, on a country level, it will be ensured that up to 30 % of the population can be subjects with mild disease (based on the PGA performed at Baseline), as monitored by data management. It is planned that the data from trial sites that participate in this trial will be combined so that an adequate number of subjects will be available for analysis. Trial sites yielding fewer than 14 subjects overall will be combined in order of geographical proximity. The exact composition of these "analysis sites" will be determined and documented prior to breaking the trial blind. In statistical models, site will refer to trial site or analysis site, if combination of trial sites is needed.

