8.4 Estimands

The efficacy endpoints will be analyzed focusing on two different estimands:

Primary estimand (treatment-policy): the effect of initiating the treatment regimen in subjects with mild-to-moderate psoriasis, with or without any other psoriasis treatment, and whether or not the subject adhered to the treatment regimen.

Thus, for the treatment-policy estimand all available data will be used.

Secondary estimand (hypothetical-strategy): the expected effect in subjects with mild-to-moderate psoriasis if all subjects adhered to the treatment regimen and did not take any other psoriasis treatment (=treatment that according to medical judgement may improve psoriasis).

This is interpreted in the sense that subjects did not initiate other treatment that according to medical judgement may improve psoriasis, and for visits after baseline adhered to the treatment schedule defined as application of IP as specified by the investigator at the previous site visit for at least 70% of the days from baseline visit to Week 4, Week 4 to Week 6 and Week 6 to Week 8. For example, applying IP for 10 out of 14 days is considered adherence, while 9 out of 14 days is not. Thus, for the hypothetical-strategy estimand, only data at or prior to use of other treatment that may improve psoriasis according to medical judgement, and prior to non-adherence to treatment schedule is used. Missing data, data after use of other psoriasis treatment, and data after non-adherence is imputed.

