Efficacy endpoints will be analyzed by different estimands, following a treatment-policy strategy (primary estimand) and a hypothetical strategy (secondary estimand). Only on PTCS, a while-on-treatment strategy will be followed.

According to the *treatment-policy strategy*, all available data will be used, regardless of treatment and treatment adherence. Missing data will be imputed.

According to the *hypothetical strategy*, only data will be used under the IP and while adhering to the IP. If any other psoriasis treatment is used, i.e. treatment that according to medical judgement may improve psoriasis, data during and after the period of other psoriasis treatment intake is invalid and will not be used. Furthermore, data will not be used of periods of potential non-adherence to the IP. Non-adherence will be given if the IP is applied on less than 70% of the days from Day 0 to Week 4, Week 4 to Week 6, and Week 6 to Week 8, respectively. Non-adherence to the IP is derived from days with treatment non-compliance. Missing and invalid data will be imputed.

According to the *while-on-treatment strategy*, all available data will be used with treatment within 7 days before assessment. Data without treatment within 7 days before assessment is invalid and will not be used.

Hierarchical testing applies to the primary analyses per endpoint, not to any sensitivity analyses as described below.

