5.5.1 Primary Efficacy Endpoint

The primary endpoint, percentage change in mPASI on the body (trunk and/or limbs) from baseline to Week 8, will be analysed for superiority and non-inferiority by means of ANCOVA as described in Section 5.4.2.

Primary Analysis

The primary analysis is for superiority of MC2-01 cream versus MC2-01 cream vehicle and of active comparator versus MC2-01 cream vehicle as well as for non-inferiority of MC2-01 cream and active comparator using the treatment-policy strategy on the FAS using MI to impute missing data. The estimated pairwise differences will be reported together with the associated standard error, the 95% confidence interval, and p-values of testing hypotheses H_{0a} , H_{0b} and H_{0c} .

Sensitivity Analyses

Three sensitivity analyses are planned on the primary endpoint, for internal validity a tipping-point analysis following the treatment-policy strategy on the FAS using MI, for external validity an analysis following the hypothetical strategy on the FAS using MI, and an analysis following the treatment-policy strategy on the PPS.

Tipping-point analysis for treatment-policy strategy on the FAS

The primary analysis of mPASI using MI assumes that data are missing at random (MAR) within each treatment arm. For each hypothesis, the sensitivity of the MAR assumption is investigated using a tipping-point analysis [10]. A penalty (a number) is added to all imputed Week 8 values in the MC2-01 cream treatment group or (when testing superiority of active comparator vs. vehicle) in the active comparator group, and the analysis is repeated on the FAS for the treatment-policy estimand as described for the primary analysis. The penalty is gradually increased until the point, the tipping point, where the conclusion (superiority or non-inferiority depending on the analysis) no longer is demonstrated. The tipping point will be reported. If the tipping point is considered a clinical plausible difference, the tipping-point analysis does not support the primary analysis.

Hypothetical strategy on the FAS

mPASI is analysed following the hypothetical strategy as described in Section 5.3 on the FAS using MI for missing and unused data as described in Section 4.7.2.

Treatment-policy strategy on the PPS

mPASI is analysed following the treatment-policy strategy as in the primary analysis, but on the PPS without using any imputation approach.

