5.6 Changes and Clarifications to Analyses Planned in the Study Protocol

Analyses are planned according to protocol. Defined as other endpoints in the protocol, mPASI75 at Week 8 and PGA of psoriasis severity on the scalp at Week 8 are promoted to secondary endpoints at the end of the hierarchical testing strategy on secondary endpoints. For PGA on the scalp, the same definition of PGA success as on the body will be applied, on a subpopulation of subjects with psoriasis on the scalp at baseline. To clarify, BSA assessment is listed under other endpoints. Notable laboratory normal ranges will not be defined.

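### SAP 5.3 drops only the non-adherent intervals from the hypothetical-strategy sensitivity analyses, whereas Protocol 8.4 imputes everything after the first lapse; SAP 5.6 does not list the difference

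*SAP*

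**What the plan says.** Protocol 8.4 defines the secondary (hypothetical) estimand as "the expected effect in subjects with mild-to-moderate psoriasis if all subjects adhered to the treatment regimen" and took no other psoriasis treatment. Its data rule is a cut-off in time: observations before the first non-adherence are used, and "data after use of other psoriasis treatment, and data after non-adherence is imputed". It makes no exception for a subject who resumes.

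SAP 5.3 has two rules. For other psoriasis treatment, "data during and after the period of other psoriasis treatment intake is invalid and will not be used". For non-adherence, the next sentence says: "Furthermore, data will not be used of periods of potential non-adherence to the IP". Only the first rule reaches forward in time.

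Both documents use the same threshold (70% of days) and judge it in the same three intervals: baseline to Week 4, Week 4 to 6, and Week 6 to 8. SAP 2.4.3 counts non-administration with approval as compliance.

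The rule feeds a planned check on the primary endpoint, described in SAP 5.5.1 as "for external validity an analysis following the hypothetical strategy on the FAS using MI". It also feeds the second sensitivity analysis of PGA success (SAP 5.5.2; Table 5 lists it for body and scalp). SAP 5.6 opens with "Analyses are planned according to protocol". It then names changes or clarifications for mPASI 75, scalp PGA, BSA and laboratory ranges, but nothing on the hypothetical strategy.

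**The concern.** The two documents give different data rules for one estimand. A Week 8 score observed after a substantial early lapse may be worse than it would have been under full adherence, even if the subject was adherent in the last two weeks. Using that score does not match an estimand that asks what would have happened had everyone adhered. The SAP recognises carry-over for other psoriasis treatment but not for missed doses.

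What is at stake is how to read one of the three planned checks on the mPASI non-inferiority claim, and one check on PGA success. If the shares of subjects who lapse early and then resume differ between cream and gel, the analysis meant to remove adherence differences would retain part of them.

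**Working it through.** **1. The two rules, pattern by pattern.** A = adherent, N = below 70%, in Weeks 0-4 / 4-6 / 6-8.

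| Pattern | Week 8 used, SAP 5.3 | Week 8 used, Protocol 8.4 |
|---|---|---|
| A/A/A | yes | yes |
| N/A/A | yes | no |
| A/N/A | yes | no |
| N/N/A | yes | no |
| A/A/N | no | no |

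The documents part only where an early lapse is followed by an adherent (or approved-stop) Weeks 6-8. A lapse in Weeks 6-8 itself leads to imputation under both.

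**2. The plan's own figure.** Protocol 8.2 gives SD 38, 204 per active arm, margin 12, true difference 0 and power 88.9%. SE = 38 × √(2/204) = 3.763. Power = Φ(12/3.763 − 1.96) = Φ(1.229) = 89.05%; the noncentral t with 406 df gives 88.91%. The figure reproduces, and nothing here changes it. The SE serves only as a yardstick.

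**3. Size, by assumption.** Count reductions as positive. Let s be the share of an arm that lapses early and resumes, and L their average Week 8 loss. Assume that imputation under the protocol rule recovers the adherent value. The SAP rule then lowers an arm's mean by s × L, so

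shift of (cream − gel) towards cream = (s_gel − s_cream) × L.

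The documents give neither s nor L. The planning effect in Protocol 8.2 is 56 − 27 = 29 points; a quarter is 7.25 and a half is 14.5.

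| s_gel − s_cream | L = 7.25 | L = 14.5 |
|---|---|---|
| 0 | 0 | 0 |
| +0.05 | 0.36 | 0.73 |
| −0.05 | −0.36 | −0.73 |

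If cream were truly 12 points worse under adherence, this check would pass with probability Φ(−1.96 + shift/3.763): 2.5% at 0, 3.1% at 0.36 and 3.9% at 0.73. Shares of 5% and 10% correspond to about 10 and 20 of 204 subjects.

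**4. What the per-protocol analysis already removes.** SAP 4.2.3 requires 80% of days over Weeks 0-8 and 80% over Weeks 4-8. Take 56 and 28 days, with no doses missed outside the lapse.

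- Weeks 0-4: non-adherence starts at 9 missed days (19/28 = 67.9%; 8 missed gives 20/28 = 71.4%). Overall compliance is 47/56 = 83.9% at 9 missed, 45/56 = 80.4% at 11 and 44/56 = 78.6% at 12. Subjects missing 9-11 days stay in.
- Weeks 4-6: non-adherence starts at 5 missed days (9/14 = 64.3%; 4 missed gives 10/14 = 71.4%). Weeks 4-8 compliance is 23/28 = 82.1% at 5 missed and 22/28 = 78.6% at 6. Only subjects missing exactly 5 days stay in.
- Both intervals: at least 9 + 5 = 14 missed gives at most 42/56 = 75.0%, so these subjects fail.

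The moderate lapsers who stay in keep their observed Week 8 score in the primary, per-protocol and, under the SAP wording, hypothetical analyses. Only the protocol rule takes it out of one of them.

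**5. Precision cost of the protocol rule.** Suppose 5% of cream and 10% of gel subjects lose their Week 8 score at random and earlier visits recover nothing. Then SE = 38 × √(1/(204 × 0.95) + 1/(204 × 0.90)) = 3.91, about 4% above 3.76. A simulation at these shares had lapses at random in Weeks 4-6 and imputed Week 8 from Weeks 1 and 4, with assumed visit correlations of 0.45 to 0.85. It gave 3.78 under the SAP rule and 3.84 under the protocol rule, about 2% more.

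**The case against.** **The conflict is inferred.** No SAP sentence says that Week 8 is kept after an earlier lapse. The SAP introduction asks to be read with the protocol, SAP 5.6 affirms agreement with it, and SAP 5.7 leaves technical detail to programming specifications that are not in these documents. It stands that nobody can tell from the text what will be programmed. It does not follow that there is no conflict. The SAP is not silent: it states an interval-based rule, directly after a rule that does extend forward. Protocol 8.1 also presents its own methods text as an outline for the SAP to complete.

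**The per-protocol analysis already covers this.** Largely true: heavy lapsers, for whom a large loss is most plausible, fall under its exclusion criteria. The gap is the band of moderate lapsers in step 4.

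**Direction.** A reader might infer that the SAP rule favours cream, because Protocol 2.3 says a cream may bring "improved convenience and ease of use resulting in increased patient adherence to therapy which will improve real-life treatment outcome". That is an expectation about a formulation in practice, not adherence data from a trial. With equal shares the bias is zero, and if more cream subjects lapse it works against cream.

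**Size.** A reader might also take the loss as the full 29 points and the share difference as 10 percentage points. That gives 0.10 × 29 = 2.9 points, 24% of the margin, and a pass probability of 11.7%. It requires resumed subjects to do no better than vehicle after at least 70% of doses (or an approved stop) in Weeks 6-8, plus a share difference with no support in the documents. It is an extreme case only.

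**The remedy has its own assumption.** If lapsing is related to response, missing-at-random imputation is biased too. After a Weeks 0-4 lapse, Week 8 must be imputed from baseline variables and site alone. This stands as a cost. It is not a new kind of assumption, since the planned imputation already makes it, and both rules already discard the scores inside that first interval.

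**Conclusion.** The inconsistency is real and minor. As written, SAP 5.3 retains Week 8 scores that Protocol 8.4 imputes and that may not fit a full-adherence estimand, and SAP 5.6 does not disclose this.

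The reach is limited to the hypothetical-strategy sensitivity analyses of mPASI and PGA success. A reader might infer that the trial's type I error or its main conclusion is at risk. It is not: the primary analysis uses all available data whatever the adherence, and SAP 5.3 keeps the hierarchy to the primary analyses. The pass probabilities above describe a supporting check to which no decision rule is attached.

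Direction and size cannot be determined from the documents. Under the stated assumptions (shares differing by 5 percentage points, a quarter to half of the planning effect lost, imputation otherwise valid), the cream-gel shift is about 0.4 to 0.7 points in either direction, against a margin of 12. The case for acting rests on the mismatch and the low cost of removing it, not on a demonstrated bias.

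**What to change.** Before unblinding, replace the SAP 5.3 sentence on non-adherence with: *Furthermore, data during and after the first interval with non-adherence to the IP are invalid and will not be used.* The multiple imputation in SAP 4.7.2 then applies unchanged. If the sponsor prefers the interval-based rule, SAP 5.6 should list it as a departure from Protocol 8.4 and give the reason.

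The change needs one sentence, no protocol amendment and no new data. More Week 8 values are imputed under missing-at-random, with little information to draw on after a Weeks 0-4 lapse. The standard error of this check rises by roughly 2%, and by at most about 4% at the shares illustrated.

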5.4 Approaches for Analysis

All collected, recorded and derived data for analysis will be listed in individual subject data listings. On vital signs, notably abnormal values will be flagged.

5.4.1 Categorical Data

Categorical data will be described by summary tables of counts and percentages. This includes zero counts of all possible categories, if any. Selected categorical variables will be visualized by bar charts by treatment group and visit.

Logistic Regression

Selected binary endpoints will be analysed using a logistic model with effects of treatment, analysis site, and the baseline value of the endpoint as factors. The estimated log odds ratios between the treatments at Week 8 will be derived together with the associated standard error and 95% confidence intervals.

Logistic regression is used for superiority testing only. The non-inferiority analysis is done without modelling by means of unadjusted risk differences between treatment groups. 95% confidence intervals will be computed using normal approximation.

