6.5 Assignment to Treatment

6.5.1 Randomisation

Randomisation will be performed using a validated system that automates the random assignment of treatment groups to randomisation numbers. Treatment assignment will be via a central interactive web response system (IWRS) in accordance with a pre-planned computer-generated randomisation schedule in a 3:1:3 ratio (MC2-01 cream; MC2-01 vehicle; active comparator). Randomisation will be stratified by trial site to ensure a proper distribution into the three treatment arms. Furthermore, on a country level, it will be ensured that up to 30 % of the population can be subjects with mild disease (based on the PGA), as monitored by data management.

Randomisation data will be kept strictly confidential, accessible only to authorised persons not otherwise involved in the conduct of the trial, until the time of un-blinding.

A subject who fulfils the trial eligibility requirements will be randomly assigned to treatment.

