8.6.1.1 Analysis of primary endpoint

Superiority analysis

First the percentage change in mPASI from baseline to Week 8 for MC2-01 cream and the active comparator will be compared with that of MC2-01 cream vehicle for a superiority evaluation using the treatment-policy estimand for the ITT population and imputing missing data using MI.

The comparison will be done using an ANCOVA model including treatment, site, and baseline PGA as factors, and baseline mPASI as covariate. The estimated differences between MC2-01 cream and MC2-01 cream vehicle, and between active comparator and MC2-01 cream vehicle, will be reported together with the associated standard error, the 95% confidence interval, and a test corresponding to no difference between treatments.

Non-inferiority analysis

Next, if and only if superiority to MC2-01 cream vehicle can be claimed for both MC2-01 cream and active comparator on the 5% significance level, MC2-01 cream will be compared to active comparator for a non-inferiority evaluation using the treatment-regimen estimand for the ITT population and imputing missing data using MI.

Percentage change in mPASI from baseline to Week 8 will be compared between MC2-01 cream and active comparator for a non-inferiority evaluation using the -12 percentage points non-inferiority margin. The comparison will be done using the same model as applied for the analysis of superiority vs. vehicle as described above: an ANCOVA model including treatment, site, and baseline PGA as factors, and baseline mPASI as covariate. The estimated difference between MC2-01 cream and active comparator will be reported together with the associated standard error, and the 95% confidence interval. If the lower limit of the 95% confidence interval is above -12 percentage points, non-inferiority is demonstrated.

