8.6.2 Secondary Efficacy Endpoints

The secondary efficacy endpoints are:

- PGA success on the body (trunk and/or limbs) at Week 8
- Subject assessment of treatment convenience at Week 8 using the PTCS Analysis of secondary endpoints

To control the global Type-I error, the secondary endpoints will be tested in hierarchical order, if and only if non-inferiority can be demonstrated for the primary endpoint. The endpoints will be analyzed using the treatment-regimen policy estimand for the ITT population.

For PGA success, missing PGA values will be imputed using MI considering PGA as a continuous endpoint.

• PGA success: PGA success of both MC2-01 cream and active comparator will be compared with that of MC2-01 vehicle for a superiority evaluation. The comparison will be done using a logistic model with treatment, baseline PGA, and site as factors.

Clinical Trial Protocol

MC2-01-C7

16 October 2018 Version 2.0

- PGA success: Non-inferiority of MC2-01 cream versus active comparator. PGA success will be compared between MC2-01 cream and active comparator for a non-inferiority evaluation using a -10 percentage points non-inferiority margin, as -10 percentage point is considered the largest clinically acceptable loss of effect. This non-inferiority margin was also used in the MC2-01-C2 trial (1). The percentage of subjects in each group with treatment success will be calculated along with its 95% confidence interval (CI) using normal approximation. A 95%, 2-sided CI for PM-PA, where PM and PA are the PGA treatment success rate at Week 8 for MC2-01 cream and active comparator respectively, will be computed using normal approximation using Proc FREQ with RISKDIFF option. MC2-01 will be considered non-inferior to active comparator if the lower bound of the 2-sided 95% CI is ≥ -10% points.
- PCTS: Superiority of MC2-01 cream versus active comparator. A PCTS score is considered invalid, if subject has discontinued study medication more than 7 days prior to the day of assessment. Missing and invalid PTCS scores will be imputed using the last valid measure prior to the visit (LOCF). This approach corresponds to a "PCTS while on treatment" estimand. The PCTS score will be compared between MC2-01 cream and active comparator using an ANCOVA model with treatment, baseline PGA, and site as factors.

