4.3 Subgroups and Confounding Factors for Analysis

No subgroup analysis will be done.

The potential confounding by trial sites will be considered by adjustment in statistical models. By country, trial sites with less than 14 FAS subjects will be pooled to form *analysis sites*. For trial sites with 14 FAS subjects or more, the trial site will be the analysis site.

The potential confounding by PGA at baseline will be considered by adjustment in all statistical models.

Depending on the endpoint as described below, the analysis may be adjusted by further confounding factors, particularly the baseline values of the respective endpoints in the models as covariates.

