5.2 Statistical Hypotheses

Let μ_M , μ_V and μ_C be estimators of treatment effect per endpoint for MC2-01 cream, MC2-01 cream vehicle and active comparator, respectively. The following four statistical hypotheses will be tested.

- a. H_{0a} : $\mu_M = \mu_V$ versus H_{1a} : $\mu_M \neq \mu_V$,
- b. H_{0b} : $\mu_C = \mu_V$ versus H_{1b} : $\mu_C \neq \mu_V$,
- c. H_{0c} : $\mu_M \mu_C \le -\Delta$ versus H_{1c} : $\mu_M \mu_C > -\Delta$,
- d. H_{0d} : $\mu_M = \mu_C$ versus H_{1d} : $\mu_M \neq \mu_C$.

where Δ is a non-inferiority margin. In two-sided H_{0a}, H_{0b} and H_{0d}, if the hypothesis is rejected, superiority of the group with greater estimate is concluded. On one-sided H_{0c}, if the lower limit of the two-sided 95% confidence interval of the estimate of the treatment difference is greater than - Δ , non-inferiority of MC2-01 cream as compared to active comparator is concluded.

The non-inferiority margin Δ is 12 percentage points on the primary endpoint mPASI and 10 percentage points on the first secondary endpoint PGA success.

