5.3 Overall Strategy and Issues of Multiplicity

The statistical hypotheses on the primary and secondary endpoints will be tested confirmatorily in a hierarchical approach. The hierarchical approach ensures that the familywise type 1 error is controlled. According to the definitions in Section 5.2, hypotheses will be hierarchically tested starting with H_{0a} and H_{0b} . If, and only if H_{0a} and H_{0b} are, H_{0c} is tested confirmatorily. Hierarchical testing, H_{0a} to H_{0c} , will be done on the primary endpoint, mPASI, at first. If, and only if, non-inferiority of MC2-01 cream versus active comparator is claimed on the primary endpoint, the hierarchical testing procedure is continued on the first secondary endpoint, PGA success on the body. If, and only if, non-inferiority of MC2-01 cream versus active comparator is claimed on the first secondary endpoint, H_{0d} is tested on the second secondary endpoint, mPASI 75, where also H_{0a} is tested, and the fourth secondary endpoint, PGA success on the scalp, if, and only if, leading to rejections on the previous steps. In case hypotheses cannot be rejected, testing on this and all preceding hypotheses is exploratory only. The strategy is summarized in the following display.

Table 4: Overview on Hierarchical Hypothesis Testing Strategy with Different Endpoints and Hypotheses

Endpoint	Step	Hypothesis
%change in mPASI at Week 8	1	H _{0a} for superiority of MC2-01 cream over vehicle
	2	H _{0b} for superiority of active comparator cream over vehicle
	3	H _{0c} for non-inferiority of MC2-01 cream and active comparator
PGA success on the body at Week 8	4	H _{0a} for superiority of MC2-01 cream over vehicle
	5	H _{0b} for superiority of active comparator cream over vehicle
	6	H _{0c} for non-inferiority of MC2-01 cream and active comparator
PTCS at Week 8	7	H _{0d} for superiority of MC2-01 cream over active comparator
%change in mPASI at Week 8	8	H _{0d} for superiority of MC2-01 cream over active comparator
PGA success on the body at Week 8	9	H _{0d} for superiority of MC2-01 cream over active comparator
mPASI 75 at Week 8	10	H _{0a} for superiority of MC2-01 cream over vehicle
	11	H _{0d} for superiority of MC2-01 cream over active comparator
PGA success on the scalp at Week 8	12	H _{0a} for superiority of MC2-01 cream over vehicle
-	13	H _{0d} for superiority of MC2-01 cream over active comparator

For definitions of hypotheses, see Section 5.2

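### Step 6, the PGA-success non-inferiority test that gates PTCS, ignores baseline PGA; standardising over it would recover up to a few points of power at almost no cost

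*SAP*

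**What the plan says.** **Step 6.** SAP 5.4.1 reserves logistic regression for superiority. For PGA-success non-inferiority it says: "The non-inferiority analysis is done without modelling by means of unadjusted risk differences between treatment groups". Protocol 8.6.2 specifies the same analysis: the confidence interval for the difference in success rates "will be computed using normal approximation using Proc FREQ with RISKDIFF option". The margin is "10 percentage points on the first secondary endpoint PGA success" (SAP 5.2).

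**Its place in the sequence.** SAP 5.3 continues to PTCS "If, and only if, non-inferiority of MC2-01 cream versus active comparator is claimed on the first secondary endpoint". Under Table 4 of the SAP, steps 7 to 13 are therefore confirmatory only if step 6 succeeds.

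**The other gating tests.** Steps 1 to 3 use ANCOVA with analysis site, baseline PGA and baseline mPASI. For the primary non-inferiority test the protocol says: "The comparison will be done using the same model as applied for the analysis of superiority vs. vehicle as described above". Steps 4 and 5 use a logistic model with analysis site and baseline PGA. SAP 4.3 states the general policy: "The potential confounding by PGA at baseline will be considered by adjustment in all statistical models".

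**The endpoint.** Protocol 4.2 counts a subject with mild disease at baseline as a success only at PGA 0, and a subject with moderate disease at PGA 0 or 1. Protocol 6.5.1 and 8.1 allow up to 30% mild subjects.

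**The concern.** A two-point fall means complete clearance for a mild subject but only almost clear for a moderate one, so baseline PGA is a natural candidate for a prognostic factor. The plan uses it in steps 1 to 5 and leaves it out of the one test that stands between the primary result and the convenience claim. If success differs by baseline PGA, the unadjusted interval is wider than it needs to be. At stake is a somewhat lower chance that a truly equal cream reaches PTCS and the later steps as confirmatory tests.

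**Working it through.** **Inputs.** From protocol 8.2: 204 per active arm, 68 on vehicle, success 30% on each active and 11% on vehicle, two-sided 5% level. From protocol 8.6.2: margin of 10 points. The split of success by baseline PGA is not in the documents and is varied below.

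**The plan's own figures.**
- Primary non-inferiority (margin 12, SD 38, 204 per arm, noncentral t with 406 df): 88.9%, as stated.
- PGA superiority to vehicle: pooled rate (204×0.30 + 68×0.11)/272 = 0.2525; null SE = sqrt(0.2525×0.7475×(1/204 + 1/68)) = 0.0608; alternative SE = sqrt(0.21/204 + 0.0979/68) = 0.0497; power = Φ((0.19 − 1.96×0.0608)/0.0497) = 92.3%. The stated 90.4% lies between this and the continuity-corrected value of 89.0%.
- No power is stated for step 6.

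**Step 6 as planned, true difference 0.** SE = sqrt(2×0.30×0.70/204) = 0.0454. Power = Φ(0.10/0.0454 − 1.96) = Φ(0.244) = 59.6%. At 20% success it is 71.4%, and at 40% it is 54.0%. For 80% power at 30% success: 2×0.21×(1.96 + 0.8416)²/0.01, or about 330 per arm.

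**Step 6 standardised over baseline PGA.** Let f be the mild share, and p_mild and p_mod the success rates, with f×p_mild + (1−f)×p_mod = 0.30. Standardising removes the between-stratum part of the outcome variance, so the variance is multiplied by

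1 − f(1−f)(p_mod − p_mild)²/0.21.

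Example with f = 0.30 and p_mild = 0.10: p_mod = (0.30 − 0.03)/0.70 = 0.386; ratio = 1 − 0.21×0.286²/0.21 = 0.918; power = Φ(2.204/sqrt(0.918) − 1.96) = 63.3%. That is equivalent to 204/0.918 = 222 per arm.

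| Mild share | Mild success (assumed) | Variance ratio | Gain in power (points) |
|---|---|---|---|
| 15% | 30% | 1.000 | 0 |
| 15% | 20% | 0.992 | 0.4 |
| 15% | 10% | 0.966 | 1.5 |
| 15% | 5% | 0.947 | 2.3 |
| 30% | 30% | 1.000 | 0 |
| 30% | 20% | 0.980 | 0.9 |
| 30% | 10% | 0.918 | 3.7 |
| 30% | 5% | 0.872 | 5.9 |

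**Simulation check** (40,000 trials per scenario, complete data). Standardising over baseline PGA alone lost only 0.1 to 0.2 point when baseline PGA was not prognostic, and gained just under 6 points in the most favourable case. At a true difference of −10 points, one-sided error was 2.3 to 2.7%, against 2.3 to 2.6% unadjusted.

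**Does analysis site add anything?** A separate simulation had 4,000 trials per scenario, 34 sites pooled by country under 14 subjects, and an assumed 6 countries. With no site effect, 30% mild and 10% mild success, site plus PGA gave 63.5% and PGA alone 63.7%. Site terms helped only with an assumed site SD of 0.6 on the logit scale: 65.4% against 64.4% at 30% mild, and 62.0% against 60.1% at 15% mild.

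**The case against.** The planned test is simple, valid and specified identically in both documents. The gain depends on success rates by baseline PGA that the plan does not give, and it could be nil. The 30% mild share is a cap, and at 15% the gain is about 2 points at most. The near-6-point figure needs mild success of 5% against 40.7% in moderate subjects, an eightfold contrast. All of this stands, and it limits the point to one of efficiency.

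A reader might infer that the SAP contradicts itself, because section 4.3 promises adjustment for baseline PGA. It does not: 4.3 speaks of statistical models, and 5.4.1 says that this analysis uses none.

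A reader might also argue that analysis site belongs in the adjustment, since randomisation is stratified by site. That would be permissible but is not needed for the gain. It would also bring a sparse-data problem: after the planned pooling, at least one analysis site had no successes in about 13% of simulated trials without a site effect, and in about 33% with a site SD of 0.6. A merging rule driven by success counts is awkward to define across 100 imputed datasets. Baseline PGA alone avoids it.

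**Conclusion.** Step 6 is a valid but mildly inefficient test at a gating position. Standardising over baseline PGA would raise its power by about 0 to 2 points at 15% mild and 0 to 6 points at 30% mild. If baseline PGA is not prognostic, essentially nothing is lost. These figures assume 30% success in both active arms, no true difference, complete data on 204 per arm, and mild success between 5% and 30%. Missing data would lower power with either method.

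Two stronger readings are not supported. The unadjusted difference is not biased and does not inflate type I error. Nor does adjustment cure the low power of step 6, which stays at about 60 to 66% at the plan's 30% rate. That level follows from a 10-point margin with 204 per arm in a trial sized on mPASI, not from the missing covariate.

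**What to change.** Before unblinding, make the step 6 primary analysis a risk difference standardised over baseline PGA:

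- Take the cream-minus-comparator difference in success rates within the mild and moderate strata. Weight these by the combined baseline PGA distribution of the two active arms.
- Compute the estimate and its standard error in each imputed dataset, pool by Rubin's rule, and compare the lower 95% limit with the unchanged −10 point margin.
- Keep the unadjusted RISKDIFF result as a sensitivity analysis and as the fallback if the PGA strata cannot be used. State in advance, on blinded data, when that applies.
- Leave analysis site out, or name it as optional. No site-merging rule is then required.
- Record the change in SAP 5.6, which now says that the analyses follow the protocol. Amend the protocol if its section 9.1 requires it.

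The cost is minor programming and a documented departure from the Proc FREQ RISKDIFF wording in protocol 8.6.2. Sample size, margin, data collection and testing order do not change.
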